## **Safety Assessments**

This study does not involve any new treatments of care, but rather focuses on standard care delivered in a new way. It is possible that the interventions will result in better compliance with medication treatment, resulting in over-control of diabetes or blood pressure. This could result in low blood sugar or low blood pressure and resultant symptoms. Therefore, we will monitor potential adverse events of this nature. We will monitor symptoms of low blood sugar in both trial arms at the follow-up data collection point as well as at ongoing contacts during the 12-week intervention phase, by peer coaches. During these contacts, symptoms of low blood sugar and low blood pressure will be assessed and reported to the investigators and to the participant's physician. If symptoms are present, the peer coach will refer participants to their primary care provider for evaluation immediately, assisting with the telephone call if needed.

Data on safety endpoints will be reviewed by a board convened for this purpose. Quarterly reports will be presented to the board over the course of the trial. The board will be constituted by 3 individuals experienced in the conduct of clinical trials and the safety of human subjects. Adverse events will be reported to the UAB IRB, and the NIH Office of Biotechnology Activities (OBA) in accordance with regulations, by the PI.

[name] and project investigators, including our community team members, will have an initial organizational meeting or conference call to discuss the protocol development, review of scientific, safety and ethical issues

related to the study design and approve plans for data integrity. After the initial planning meeting project investigators will be convened monthly in a meeting or conference call throughout the project period.

[name] will be responsible for monitoring the safety and efficacy of the study, executing the data and safety monitoring plan, and complying with the reporting requirements. She will provide a summary of the DSM report to PCORI on an annual basis as part of the progress report. The report will include participant's sociodemographic characteristics, expected versus actual recruitment rates, any quality assurance or regulatory issues that occurred during the past year, summary of adverse events, and any actions or changes with respect to the protocol. The DSM report to PCORI will also include, when available, the results of any efficacy data analysis conducted.

Project investigators will be primarily responsible for protecting the safety of the study participants and the scientific credibility of the project, and the validity of the assessment of the efficacy of the interventions used in the projects. The project investigators will also formulate recommendations relating to the selection, recruitment and retention of participants, their management, improving adherence to protocol-specified regimens, and the procedures for data management and quality control.

The entire project team will monitor success of recruitment, assess data integrity, and most importantly monitor for adverse events. Risks to study participants relate mostly to misinterpretation of what is research and what is usual care and loss of confidentiality. Project investigators will carefully evaluate how the study is described and assure that study subjects are informed not to report urgent symptoms (chest pain) through email communications. Any hospitalizations or deaths discovered by the research team will be promptly reported to the DSMB with an assessment of whether any study procedures may have contributed to these outcomes.

The risks of the study are low, and thus the safety monitoring plan has been matched to the risk to subjects in this study. Risks to physician study participants relate mostly to misinterpretation of what is research and what is usual care and loss of confidentiality. We are encouraging physicians and their staff to increase their provision of care related to diabetes, osteoarthritis and chronic pain to be consistent with current guidelines. However, we are not asking the physicians or their staff to provide services beyond those in standard, high-quality medical practices.

For this study, we plan interim data analysis twice annually to assess probability of statistically significant group differences. We will first compare baseline data to assure adequacy of randomization. We will then conduct interim analyses that will coincide with practice data intervals, and set intervals for patient data collection for outcomes data. Prior to interim analyses, investigators will assign stopping rules. Safety data to be included in these reports include hospitalization rates as well as Emergency Room utilization.

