## Study Design

We will compare usual care to viewing an educational DVD including peer storytelling and a 6-month telephone-delivered peer coaching intervention. We propose to use an RCT design because we aim to test the effectiveness of the intervention on medication adherence and A1c, blood pressure and cholesterol.

The trial will be cluster-randomized to reflect the clustering of patients within tightly knit small rural communities. People talk frequently within these communities, and if two participants from the same town are in different trial arms and compare notes, this could change their behavior and threaten the validity of the study. Each of the anticipated 80-100 towns will therefore be group-randomized in blocks to avoid contamination across trial arms. We considered using physician practices as clusters, but we have learned that it is common for different family members to attend different practices many miles from home.

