### **Intervention participants also receive 13-16 telephone contacts from a Peer Advisor.**

Months 1-3 are the intensive phase. During the first 8 weeks of the intensive phase, peer advisor contacts will occur weekly. During weeks 9-12, the peer contact will occur bi-weekly.

Months 3-6 are the maintenance phase. During this phase, the peer contacts will occur monthly. No new content areas are introduced. Participant will continue to work on the goals set during the first 3 months of the program. The peer advisor will call monthly during the "check-in session". During these sessions, the peer and participant will review goals set, goal progress, assess barriers and help problem solve barriers. If participant is having trouble with their health goals during this phase, the peer and participant can decide that more contacts than monthly contacts are needed. For these participants, the peer advisor will provide a 'mini-intensive' phase, during which calls will be increased to weekly.

The participants will be allowed to telephone the peer advisors with questions or concerns between sessions. During session 1, the peer advisor makes sure that the participant has the correct contact number. The peer will let the participant know that it's okay to call between sessions if they have questions. They will let them know that they may not be able to take the participant calls all the time, but the peer will return their calls as soon as they can.

The schedule and topics for each week are listed below.

Mon	Week	Session Topic	Mon	Week	Session Topic
1	1	Introduction to the program, diabetes basics	4	13	No session*
	2	Healthy eating		14	No session*
	3	Physical activity		15	No session*
	4	Diabetes medications		16	Check-in session 3 (no new topic)
2	5	Blood pressure & cholesterol medications	5	17	No session*
	6	Stress and your health		18	No session*
	7	Check-in session 1 (no new topic)		19	No session*
	8	Practice and planning for the future, part 1		20	Check-in session 4 (no new topic)
3	9	No session	6	21	No session*
	10	Check-in session 2 (no new topic)		22	No session*
	11	No session		23	No session*
	12	Practice and planning for the future, part 2		24	Check-in session 5 (no new topic)

*Months 1-3 = Intensive phase; Weeks 1-8 weekly contact; weeks 9-12 biweekly contact*

*Months 4-6 = Maintenance phase; monthly contacts*

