3. During this visit, we will also make a list of all medications the participant is currently taking.
4. Provide participant with health report card

After the completion of the in-person data collection, the participant will be given the materials for the program. If the participant is in the control condition, they will be given a general health education DVD. Participants in the intervention condition will be matched with their peer advisor and given an activity book that they will use during their sessions with their peer advisors. All participants will receive their portable DVD player at the end of the data collection visit. Participants will receive a Health Report Card that provides their a1c, LDL-cholesterol, blood pressure, and weight data. If needed, participant in the intervention arm will receive a study phone.

Participants will be asked by the research staff at the in person data collection visit if they would like to use a study phone. Study phones will be taken back at the 2nd in-person study visit. Copies of the consent, in-person data collection form, and Health report card are included in Appendix F.

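### Coach checks for symptoms of low blood sugar and low blood pressure are stated only for a 12-week phase of a 24-week coaching programme, and the follow-up assessment expressly names only low blood sugar

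*Combined protocol and SAP*

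**What the plan says.** Safety Assessments, in the combined protocol and SAP, accepts that better adherence could over-control diabetes or blood pressure. It commits in general, with no time limit, to monitoring for the resulting events. The specific arrangement follows in one sentence. It opens "We will monitor symptoms of low blood sugar in both trial arms" and places this "at the follow-up data collection point as well as at ongoing contacts during the 12-week intervention phase, by peer coaches". The next sentence adds: "During these contacts, symptoms of low blood sugar and low blood pressure will be assessed and reported to the investigators". Action then depends on what is found: "If symptoms are present, the peer coach will refer participants to their primary care provider for evaluation immediately".

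The length of coaching is given elsewhere. Study Design describes "a 6-month telephone-delivered peer coaching intervention". The schedule in the Living Well with Diabetes Program Description has calls every week in weeks 1 to 8, then in weeks 10 and 12, and then "Months 4-6 = Maintenance phase; monthly contacts", at weeks 16, 20 and 24. A participant who struggles with health goals in the maintenance phase can be given a mini-intensive period "during which calls will be increased to weekly". The stated content of maintenance calls is goals, progress and barriers; symptoms are not mentioned.

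**The concern.** The plan identifies two harms and relies on coaches to pick them up between visits, but the window it gives the coaches is half as long as the coaching. The only 12-week block in the schedule is the intensive phase. Read literally, coaches ask about symptoms up to week 12 and then make at least three more calls with no stated duty to ask. The referral sentence has no time limit of its own, but it operates only after symptoms have come to light.

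A participant who becomes symptomatic soon after week 12 could therefore wait until the month-6 follow-up for the next enquiry that the plan states. For low-pressure symptoms, even that enquiry is uncertain, because the follow-up clause names low blood sugar alone. This also matters for the control arm. Coaches are assigned only on the intervention side ("Participants in the intervention condition will be matched with their peer advisor"), so follow-up is the one place where Safety Assessments could provide a symptom enquiry for controls.

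**Working it through.** **Inputs**
- Coach symptom-check window: 12 weeks (Safety Assessments).
- Programme length: 6 months, laid out as weeks 1 to 24 (Study Design; Living Well with Diabetes Program Description).
- Scheduled coach calls: weeks 1 to 8, 10, 12, 16, 20 and 24 (same schedule).
- Stated total of coach contacts: 13 to 16 (heading above that schedule).

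**Reproducing the plan's own count**
- By week 12: 8 + 2 = 10 calls.
- After week 12: 3 calls (weeks 16, 20, 24). This agrees with the week-12 session in the Peer Advisor Manual (Appendix C), which tells the participant that three scheduled calls remain.
- Total: 10 + 3 = 13, the lower end of the stated range.

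**Share outside the stated window**
- Scheduled calls: 3/13 = 23%.
- If the total reaches 16 and all 3 extra calls fall after week 12 (an assumption, although mini-intensive calls do belong to the maintenance phase): (16 − 10)/16 = 6/16 = 37.5%.
- Calendar time: (24 − 12)/24 = 50%.
- Interval from the last covered call to the end of the programme: 24 − 12 = 12 weeks. It may be somewhat longer in practice, because Participant Retention has the intervention arm's follow-up arranged after the final coach session.

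**Which symptoms, and where**

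| Occasion | Low blood sugar | Low blood pressure |
|---|---|---|
| Coach contacts to week 12 | stated | stated |
| Coach contacts in weeks 13 to 24 | not stated | not stated |
| Month-6 follow-up | stated, both arms | only if the contacts meant in "During these contacts, symptoms of low blood sugar and low blood pressure will be assessed and reported to the investigators" include follow-up |

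**Scripts in Appendix C**
- The week 1 to 12 scripts contain general side-effect questions: for each diabetes medicine in Session 1, and in Session 5 for blood pressure medicines when the reading is high. The week-5 review is tied to missed doses, and neither session names low-sugar or low-pressure symptoms.
- In Session 4, low sugar appears as part of a story from the video, not as a question about the participant.
- The visible part of the week-16 script covers homework, troubleshooting and scheduling.

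The specific question is therefore missing from the visible scripts both inside and outside the 12-week window.

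**The case against.** The strongest reply is that Safety Assessments never says checks stop at week 12. Its general commitment covers both harms without a time limit, and the 12-week wording looks like a leftover. The Peer Advisor Manual also mixes 12 weeks (Client Information) with six months (Scheduling Session 1), and Safety Assessments itself mentions osteoarthritis and chronic pain, which are not this trial's subject. Other channels stay open: participants may phone their coach, staff retention calls are made in both arms, blood pressure is measured at the in-person visit, and hospital and emergency use is tracked. The section also says that monitoring is matched to a low level of risk.

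Much of this stands. A reader might infer that participants are unmonitored after week 12; the general commitment and these channels rule that out. What is missing is a planned symptom question, and a leftover phrase can still be followed literally.

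Three further inferences go too far:
- *The week-16 script confirms a stop at week 12.* It does not. The week 1 to 12 scripts lack a specific symptom question too, so its absence at week 16 does not discriminate.
- *The gap falls where the study itself drives treatment up.* The prompt to ask the doctor for more diabetes medicine is a week-4 activity based on the baseline A1c, and the main blood pressure prompts come in week 5. Both lie inside the window. Nothing cited places study-prompted intensification after week 12.
- *Unequal questioning will bias a safety comparison between arms.* No between-arm comparison of symptom reports is described. Controls receive staff calls in months 1, 3 and 5, and those scripts were not available.

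The remainder of the week-16 script, the week-20 and week-24 scripts, the Client Plan Book, the interview, the follow-up forms and the retention scripts were also not available. Any of them could contain a symptom question.

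**Conclusion.** The mismatch is real and should be corrected. The one specific coach check covers 12 of 24 weeks, leaving 3 of 13 scheduled calls (23%, or up to 37.5% under the assumption above) and any mini-intensive calls without a stated check for harms that the plan itself names. Low-pressure symptoms at follow-up are ambiguous rather than excluded.

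The mismatch in Safety Assessments does not depend on the unseen material. The statement that later calls carry no symptom check holds only for the text available. How many symptom events would be affected is unknown, and no number is claimed. This is a safety-monitoring point; it does not bear on the efficacy analysis.

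**What to change.** 1. Reword Safety Assessments so that coach symptom checks, reporting and referral apply at all coach contacts through week 24, including mini-intensive calls.
2. In the same section, state that symptoms of both low blood sugar and low blood pressure will be asked about at the month-6 follow-up in both arms.
3. Check the tools not available here. If they lack one, add a direct question on each kind of symptom to the coach scripts at every week. Correcting only the later scripts would leave weeks 1 to 12 relying on general side-effect questions.

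The cost is a short protocol edit, one or two follow-up items, a minor script update and a briefing for coaches, for which the existing weekly group calls could serve. The documents give no figure for the added call time. Assuming about one minute per call, it comes to 13 to 16 minutes per intervention participant over the whole programme.

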### Secondary Outcomes

Secondary outcomes will be health-related quality of life and self-efficacy. *Quality of life* will be assessed through the validated Short-Form 12 (SF-12), a generic measure of health-related quality of life. We will assess diabetes-specific quality of life using the validated Diabetes Distress Scale. *Self-efficacy* in taking medications will be assessed using the Self-efficacy for Appropriate Medication Use and the Perceived Diabetes Self-Management Scale, which is associated with A1c.

We will also assess the number of physician office visits, hospital stays and emergency visits in the previous 6 months, but do not anticipate that the short duration of the study will be able to detect significant differences between trial arms. Nevertheless, we will collect these data to build toward future longer term intervention studies. In addition, during the in-home visit we will transcribe the name and dose of all diabetes, blood pressure and lipid medications at baseline and follow-up to detect whether regimens have been intensified as a result of exposure to the interventions.

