## Program Descriptions

### Control Participants: General Health Videos

Participants in the control arm will receive a general health education DVD and handout. The DVD contains videos on the following topics: Dementia and Alzheimer's, Breast Cancer, Colorectal Cancer, Osteoporosis and Fall Prevention, Eye Health, Oral Health, Foot Care, and Driving Safety. A copy of the handout is included as Appendix A.

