## Participant Retention

During the 6 months of the trial, UAB staff will contact all participants 2-3 times. During these brief 5-minute calls, the staff will answer participant questions, update contact information, and provide help if needed in accessing study education materials. Participant retention plan will be a mixture of telephone and mail contacts as shown below:

Month	Control Participants	Month	Intervention Participants
1	Phone Call: Welcome to the study, answer questions	1	No contact
2	Postcard: Reminder to look at videos	2	Phone Call: answer questions, identify problems, update contact information
3	Phone Call: answer questions, identify problems, update contact information	3	No contact
4	Postcard: Keep in touch post card card	4	No contact
5	Phone Call: answer questions, identify problems, update contact information	5	Phone Call: answer questions, identify problems, update contact information
6	Postcard: reminder of upcoming data collection	6	No contact
All participants will receive postcards for birthdays, holiday cards (Thanksgiving, Christmas)			

During month 6 (control participants) or after the final session with the peer advisor (intervention participants), study staff will contact the participant to schedule their follow-up telephone interview and in-person data collection. Copies of postcards and telephone contact scripts are included in Appendix G.

The figure below shows the study flow from recruitment to the completion of the study.

LivingWell-FlowChart-v.2016-01-12

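### Low-pressure symptoms, part of a harm the plan itself names, have no described check in the control arm; low-sugar symptoms are checked equally only at follow-up

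*Combined protocol and SAP*

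**What the plan says.** Safety Assessments recognises that better medication-taking could go too far, "resulting in over-control of diabetes or blood pressure", with symptoms as the result. The monitoring that follows has three parts.

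- For low blood sugar: "We will monitor symptoms of low blood sugar in both trial arms at the follow-up data collection point as well as at ongoing contacts". The sentence places the ongoing contacts in the 12-week intervention phase and assigns them to peer coaches.
- Next: "During these contacts, symptoms of low blood sugar and low blood pressure will be assessed and reported to the investigators", and to the participant's physician. This is the only mention of a check for low-pressure symptoms.
- Then: "If symptoms are present, the peer coach will refer participants to their primary care provider for evaluation immediately".

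The arms differ in who has a coach. Under Living Well with Diabetes Program Description, "Intervention participants also receive 13-16 telephone contacts from a Peer Advisor". For controls, "Participants in the control arm will receive a general health education DVD and handout". The Background section treats peer coach and peer advisor as the same role, and the In-Person Biometric Data Collection Visit section matches only intervention participants with an advisor.

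Some information is gathered in both arms. Staff make brief retention calls, some described as "Phone Call: answer questions, identify problems, update contact information". Under Secondary Outcomes, "We will also assess the number of physician office visits, hospital stays and emergency visits in the previous 6 months". Blood pressure and A1c are measured, and medications recorded, at baseline and follow-up.

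**The concern.** A harm can be compared between arms only if both arms are asked about it in the same way. Here the plan names two forms of the harm, low sugar and low pressure, but describes an equal symptom enquiry for only one of them, at one time point. If the forms follow the text literally, there is no control-arm figure to set beside the low-pressure symptoms that coaches report, and questions that were never asked cannot be answered later from the data.

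For low sugar the follow-up answers give a fair comparison. The risk is that a board report or final harm table also counts what coaches heard. The coached arm would then have more chances to record a symptom, and could look worse with no true difference.

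The plan specifies no between-arm symptom comparison and no data source for one. Safety Assessments promises quarterly board reports on safety endpoints, and Data Analysis covers only the efficacy and survey outcomes. What is at stake is the readability of the harm report, not the adherence result.

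**Working it through.** **1. Coach contacts.** The schedule in Living Well with Diabetes Program Description has sessions in weeks 1-8 (8), weeks 10 and 12 (2), and weeks 16, 20 and 24 (3). The total is 8 + 2 + 3 = 13, the lower end of the stated 13-16. Weeks 1-12, the phase for which ongoing checks are described, contain 8 + 2 = 10. No ongoing check is described for the other 3.

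Ten is an upper bound on scheduled occasions of enquiry. I found no worded question on low-sugar or low-pressure symptoms in the Peer Advisor Manual scripts for weeks 1-12; Session 1 asks about medication side effects in general. The number of times a coach would actually ask therefore lies between 0 and 10.

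**2. The arms side by side, as described.**

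| Enquiry | Intervention | Control |
|---|---|---|
| Low-sugar symptoms at follow-up | 1 | 1 |
| Low-sugar symptoms, ongoing, weeks 1-12 | 0 to 10 coach contacts | none described |
| Low-pressure symptoms at follow-up | none described | none described |
| Low-pressure symptoms, ongoing, weeks 1-12 | 0 to 10 coach contacts | none described |
| Staff retention calls | 2, no stated symptom check | 3, no stated symptom check |
| Measured pressure, A1c, medication list | baseline and follow-up | baseline and follow-up |
| Office, hospital and emergency visits | previous 6 months | previous 6 months |

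**3. Which contacts are meant.** The low-pressure sentence follows one that ends with the coaches' ongoing contacts, and precedes one in which the coach makes the referral. The follow-up clause names low sugar only. Coach contacts are the natural reading, though not the only possible one.

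**4. Direction and size.** With equal true rates, extra occasions of enquiry in one arm can only raise the count from any-source reports in that arm. Its size depends on how often coaches ask, how often participants say yes, how far coach reports repeat the follow-up answers, and whether the sources are combined. The documents give none of these.

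**5. Precision of an equal 6-month comparison.** Inputs from Power Calculations and Sample Size: 200 per arm after attrition, and a variance inflation factor D of 1.084 or 1.419, taken as stated. Effective n per arm = 200/1.084 = 184.5, or 200/1.419 = 140.9. With the same symptom proportion p in each arm (assumed, since none is given), the 95% half-width is 1.96 × √(2p(1−p)/n_eff):

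- p = 5%: 4.5 to 5.1 percentage points
- p = 10%: 6.1 to 7.0 points
- p = 20%: 8.2 to 9.3 points

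**The case against.** The best reply has four parts.

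- **Ambiguity and unseen forms.** The phrase 'these contacts' could cover the follow-up visit named in the preceding sentence, which would give one low-pressure check in each arm. Only part 1 of 2 of the document was available. The Client Plan Book (Appendix C) and the interview, biometric forms and retention scripts (Appendices E-G) could not be examined, and a both-arm question could well be there. This stands. It limits the point to what the protocol text describes.
- **Other both-arm data.** Blood pressure is measured by one protocol in everyone and analysed as a primary outcome, and drugs and doses are recorded at both times. Low readings and regimen changes can therefore be compared without any coach report. This stands too, but a seated reading at one visit is not a history of symptoms. Hospital and emergency visits are not specific to over-control.
- **Control calls.** Controls receive one more staff call than intervention participants, and the month 3 and 5 calls look for problems. No symptom question is stated for them.
- **Purpose.** Coach checks exist to detect and refer, and closer watching of the exposed arm is sensible for that. Agreed. The difficulty arises only if the same reports are used to compare arms.

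A reader might go further and infer that the trial will show a false excess of harm of so many points in the coached arm. The documents do not support that. Nowhere do they say coach reports will be pooled with follow-up answers, and any figure would rest on invented response rates and on independence between repeated answers from the same person.

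**Conclusion.** The point holds as a minor, cheap improvement. As the protocol text describes it, low-pressure symptoms have no control-arm comparator, and ongoing symptom enquiry is 0 to 10 scheduled contacts against none. The low-sugar comparison at follow-up is sound.

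This rests on reading the low-pressure sentence as referring to coach contacts and on the unseen appendices not already holding the question. It would be wrong to conclude that over-control cannot be compared at all, because measured pressure, A1c and regimens are available in both arms. It would also be wrong to conclude that controls will certainly never be asked about low-pressure symptoms.

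**What to change.** Add to Safety Assessments: *Symptoms of low blood sugar and of low blood pressure will be asked of all participants in both arms at the 6-month interview, with the same questions and recall period. The between-arm comparison, accounting for town clustering, will use only these answers. Symptoms reported to coaches will be used for referral and listed separately in board reports.*

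A 6-month recall period would match the one already used for health-care visits and would also cover weeks 13-24. If the interview in Appendix E already contains both questions, only the sentences on analysis and reporting are needed.

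The cost is a few lines of text and at most one interview item, with no new visits, staff or participants. There are three drawbacks. Recall over six months is imprecise. If symptoms are rare, the interval will be wide relative to the rate. Coached participants may also recognise symptoms more readily, so some difference in reporting can remain even with identical questions.
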